## **7.6 EXTENT OF EXPOSURE**

Exposure to study drug for the Safety Population during the double-blind treatment period will be summarized by treatment group in terms of treatment duration and calculated as the number of days from the date of the first dose of double-blind study drug to the date of the last dose of double-blind study drug, inclusive. Overall treatment duration will also be categorized as 1 Day; >1 Day to  $\leq 7$  Days; >7 Days to  $\leq 30$  Days; >30 Day to  $\leq 90$  Days; and  $\geq 90$  Days.

Patient-years, defined as exposure to the study drug in years, will be summarized by treatment group for the Safety Population.

## 7.7 PRIOR AND CONCOMITANT MEDICATION

Prior medication is defined as any medication taken before the date of the first dose of double-blind study drug. Concomitant medication is defined as any medication taken on or after the date of the first dose of double-blind study drug during the Treatment Period. Medications started after the date of the last dose of double-blind study drug will not be considered concomitant medications.

Both prior and concomitant medications will be coded by drug name and therapeutic class using WHO Drug Dictionary version B2 March 2015. The use of prior and concomitant medications will be summarized for the Safety Population by the number and percentage of patients in each treatment group receiving each medication within each therapeutic class. If a patient took a specific medication multiple times or took multiple medications in the same category (based on Anatomical-Therapeutic-Chemical classification), that patient would be counted only once for the coded drug name or therapeutic class. The use of per-protocol rescue medicines is collected separately the eDiary and will be summarized as described in Section 7.9.2.

## 7.8 EDIARY COMPLIANCE

Patients are required to enter their evening diary assessments into the eDiary each evening during the pretreatment and treatment period. An evening assessment is considered complete if all questions, excluding the weekly assessments, are answered.

eDiary compliance will be calculated for baseline (pretreatment period), the treatment period, and weekly. For each time period, eDiary percent compliance will be calculated as  $100 \times$  the number of completed evening reports divided by the expected number of days in the period. Percent compliance will also be dichotomized as  $\geq 80\%$  and  $< 80\%$  for each period, as well as the number and percentage of patients with  $> 4$  /  $< 4$  complete eDiary entries each week; these will be presented by treatment group for the ITT Population. Descriptive statistics (number of patients, mean, SD, median, minimum, and maximum) for eDiary compliance will be presented for the ITT population by treatment; n and percent will be presented for the dichotomous categories.

## 7.9 EFFICACY ANALYSIS

All efficacy analyses will be based on the ITT Population for key efficacy parameters.

Daily eDiary assessments collect information on BMs, including whether a BM is an SBM. SBM is defined as a BM that occurs in the absence of a laxative, enema, or suppository use on either the calendar day of the BM or the calendar day before the BM. CSBM is defined as an SBM associated with a sense of complete evacuation.

Baseline values for efficacy parameters will be derived from the eDiary daily data collected in the Pretreatment Period, specifically the period of time from 14 days prior to the day of randomization up to the time of randomization. The baseline CSBM and SBM weekly rates will be derived based on the number of CSBMs and SBMs a patient had during this period.

Baseline stool consistency and straining will be calculated as the average of the non-missing values from the SBMs reported by the patient during this period. A patient's baseline Stool Consistency and straining cannot be assessed if the patient does not have at least one SBM during the Pretreatment Period. Patients with missing baseline Stool Consistency will be excluded from Stool Consistency analyses that involve change from baseline. Similarly, patients with missing baseline straining will be excluded from straining analyses that involve change from baseline.

Baseline values for patient symptom severity parameters (e.g., abdominal discomfort, abdominal bloating, abdominal pain, abdominal symptom score [details provided in Section 7.9.2], and constipation severity) will be the average of the non-missing severity scores reported during this period.

For weekly responder parameters based on daily eDiary assessments, a patient with less than 4 complete evening reports during an analysis week will not be considered a responder for that week.

Trial centers will be pooled by geographic region (details provided in Section 9.3). In lieu of trial center, geographic region will be used in analyses adjusting for center-to-center variability.

All hypotheses will be tested at a two-sided 0.05 significance level (Section 7.9.2). All confidence intervals will be 2-sided 95% confidence intervals, unless stated otherwise.

### **7.9.1 Key Efficacy Parameter(s)**

There are 3 key efficacy parameters: 1) Weekly Change from Baseline in Abdominal Pain, 2) Weekly Change from Baseline in CSBM Frequency, and 3) 6/12 Week Abdominal Pain and Constipation (APC) +1 Responder. The criteria for each of the 3 primary efficacy parameters are provided below:

#### **Weekly Change from Baseline in Abdominal Pain**

Abdominal pain is measured daily using an 11-point NRS. A patient's weekly abdominal pain score is the average of the nonmissing abdominal pain scores reported by the patient during each week.

#### **Weekly Change from Baseline in CSBM Frequency**

A patient's weekly CSBM frequency rate is the CSBM rate (CSBMs/week) calculated over that week.

#### **6/12 Week APC +1 Responder**

A 6/12 Week APC +1 Responder is a patient who meets the Weekly APC +1 Responder criteria for at least 6 out of the 12 weeks of the Treatment Period.

- A Weekly APC +1 Responder is a patient who meets the criteria to be a Weekly CSBM +1 Responder and a Weekly Abdominal Pain Responder. If a patient did not enter information into the eDiary on at least 4 days for a particular Treatment Period week, the patient will not be considered a Weekly APC +1 Responder for that week.

- A Weekly CSBM +1 Responder is a patient who has an increase from baseline of at least 1 in the CSBM weekly rate for that week. If a patient did not enter information into the eDiary on at least 4 days for a particular Treatment Period week, the patient will not be considered a Weekly CSBM +1 Responder for that week.
- A Weekly Abdominal Pain Responder is a patient who has a decrease in the weekly average of the abdominal pain score of at least 30% compared with the baseline average. If a patient did not enter information into the eDiary on at least 4 days for a particular Treatment Period week, the patient will not be considered a Weekly Abdominal Pain Responder for that week.

### 7.9.1.1 Analyses of the Key Efficacy Parameters

All analyses of the key primary efficacy endpoints will be performed on the ITT Population.

For each continuous weekly change-from-baseline measure defined above, inferential testing of the change from baseline will be evaluated employing a MMRM framework with week (categorical), treatment, geographical region, and week-by-treatment fixed effects, and baseline value as a covariate. A compound symmetry covariance structure will be used to model the covariance of within-patient results. Exploratory analyses with unstructured and autoregressive (1) covariance structures will also be considered for planning purposes.

The overall dose response within each DR formulation will be conducted by employing an overall trend test (i.e., linear contrast, see [Appendix VI](#)) for each formulation to test for a monotonically increasing dose response within the MMRM. Overall treatment effect pairwise comparisons will be performed between each linaclotide treatment and placebo. [REDACTED]

[REDACTED]

Pairwise treatment comparisons with placebo will be performed at each week utilizing the same MMRM models.

The efficacy analysis of 6/12 Week APC+1 Responder rate will be performed by using a CMH test controlling for geographic region for each DR formulation (i.e., 1. DR1 and Placebo; 2. DR2 and Placebo). The overall trend test will be assessed via the CMH correlation statistics to test for

a monotonically increasing dose response within the formulation. Pairwise comparisons between each linaclotide dose and placebo will be performed.

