#### 4. DETERMINATION OF SAMPLE SIZE

The sample size per treatment group was determined based on a one-way design and includes 8 treatments: placebo; 30 µg, 100 µg, or 300 µg of the linaclotide DR1 formulation; 30 µg, 100 µg, or 300 µg of the linaclotide DR2 formulation; and the 290 µg dose of the linaclotide IR formulation (the FDA-approved dose for IBS-C). Previous trials with linaclotide IR demonstrated treatment differences with respect to Change from Baseline in 12-Week Abdominal Pain of 0.78 (-1.196 vs. -1.975 for placebo and linaclotide IR, respectively), and a standard deviation of 1.73 (based on the root mean squared error from an ANCOVA adjusting for baseline pain). Based on these historical values, it was estimated that, within each formulation, the highest two active treatment arms (DR1 100 µg and 300 µg; DR2 100 µg and 300 µg) would reflect the previously observed Change from Baseline (-1.975), the lowest active treatment arms within each formulation (DR1 30 µg; DR2 30 µg) would achieve a Change from Baseline of -1.586 reflecting 50% of the observed prior treatment difference (-0.39), and placebo would reflect the previously observed Change from Baseline (-1.196). Under these assumptions, a study with 65 patients per treatment arm (520 total patients) will have 81% power based on a 2-sided linear trends test within each formulation (linear contrast: -3 (placebo) -1 (30 µg) 1 (100 µg) 3 (300 µg); IR formulation not included) at an alpha level of 0.05. In addition, subsequent pairwise comparison between placebo and the active treatment groups reflecting the previously observed treatment difference will have 73% statistical power (two-sided,  $\alpha = 0.05$ ).

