### **6.2 ADJUSTING FOR COVARIATES**

As a general approach, the baseline values will be included in the mixed model repeated measures (MMRM) or analysis of covariance (ANCOVA) when the absolute or change score are analyzed. Heterogeneity of slopes will be explored (e.g., review of residuals, inclusion of an interaction term, comparison of group differences at the 25th and 75th percentiles) and, if any changes to planned analyses are needed, the change will be documented in the clinical study report.

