### 7.9.2.2 Analyses of Other Efficacy Parameters

All categorical responder parameters (e.g., Weekly CSBM +1 Responder) and CSBM (SBM) with 24-hours of first dose, will be analyzed utilizing the same methods defined above for the key efficacy measure 6/12 Week APC +1 Responder.

All continuous change-from-baseline in 12-week efficacy parameters will be evaluated using an ANCOVA model with treatment group and geographic region as fixed-effect terms and baseline value as a covariate. Least-squares (LS) means for each treatment group, LS mean differences between each linaclotide dose and placebo and their corresponding confidence intervals, and p-values for the pairwise comparisons versus placebo will be presented. [REDACTED]

[REDACTED]

For Treatment Satisfaction, inferential testing will be evaluated employing a MMRM framework with week (categorical), treatment, and week-by-treatment fixed effects, and patient as the random effect. The covariance structure will be unstructured. Pairwise comparisons between each treatment group and placebo will be performed overall and at each visit. Associated LSM means, LSM means differences and confidence intervals will be presented.

For Change from Baseline in 12-Week CSBM, SBM, Stool Consistency (BSFS and 5 point ordinal score), Abdominal Pain, Abdominal Discomfort, Abdominal Bloating, and the Abdominal Symptom Composite Score, sensitivity analyses will be performed by applying the same ANCOVA model to the rank-transformed data. Change and baseline values will be ranked based on the normalization method of Blom with ties set to the mean. If the results of the sensitivity analysis show consistency with those obtained from the original analysis, only results from the original ANCOVA will be reported.

For Change from Baseline in weekly SBM, Stool Consistency (BSFS and 5 point ordinal score), Abdominal Discomfort, Abdominal Bloating, and the Abdominal Symptom Composite Score, an ANCOVA with treatment and geographic region as fixed effects and baseline as a covariate will be fit. All pairwise comparisons performed for the 12-week analyses will be performed for each week.

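### The 6/12 Week APC+1 Responder trend test adjusts only for region; adding baseline pain and CSBM rate is a cheap improvement that may recover some power

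*SAP*

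**What the plan says.** SAP 7.9.1.1 treats the three key endpoints differently. The MMRMs for weekly abdominal pain and weekly CSBM frequency contain "geographical region, and week-by-treatment fixed effects, and baseline value as a covariate". The responder analysis is "performed by using a CMH test controlling for geographic region for each DR formulation", with the CMH correlation statistic as the trend test.

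This follows the general rule in SAP 6.2, under which baseline values "will be included in the mixed model repeated measures (MMRM) or analysis of covariance (ANCOVA) when the absolute or change score are analyzed". A responder indicator is neither an absolute nor a change score, so the rule does not reach it.

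The covariates exist. SAP 7.9 states: "The baseline CSBM and SBM weekly rates will be derived based on the number of CSBMs and SBMs a patient had during this period". Baseline pain "will be the average of the non-missing severity scores reported during this period".

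No baseline-adjusted responder analysis appears elsewhere in the visible text. The multiple-imputation analysis (SAP 7.9.1.2) recalculates the responder and repeats the same CMH. Under SAP 7.9.2.2 the other responder endpoints "will be analyzed utilizing the same methods defined above for the key efficacy measure 6/12 Week APC +1 Responder". Some text in 7.9.1.1 is redacted and Appendix VI is not shown, so neither could be checked.

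**The concern.** The responder endpoint is built from pain and CSBM frequency, the two measures whose baselines enter the continuous models. If baseline predicts who responds, a test that leaves it out carries avoidable variance and does not correct chance imbalance between arms of 65. Protocol 5.7.7.2 calls the responder analysis confirmatory of the continuous trend tests and says that a significant trend makes the formulation efficacious. No power is stated for it. At stake is efficiency on one key endpoint, recoverable from data already in the database.

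**Working it through.** **1. The plan's own power figures.** Inputs from SAP section 4: mean changes -1.196, -1.586, -1.975, -1.975; SD 1.73, "based on the root mean squared error from an ANCOVA adjusting for baseline pain"; 65 per arm; contrast -3, -1, 1, 3; two-sided 0.05.

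- Contrast: 3(1.196) + 1.586 - 1.975 - 3(1.975) = -2.726.
- SE: 1.73 x sqrt(20/65) = 0.960. Ratio 2.841.
- Trend power: Phi(2.841 - 1.960) = 81.1% (stated 81%).
- Pairwise: 0.779 / (1.73 x sqrt(2/65)) = 2.567; Phi(2.567 - 1.960) = 72.8% (stated 73%).

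Both reproduce. They concern 12-week pain change, not the responder.

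**2. Responder trend test by simulation.** From the documents: 4 arms x 65 per formulation, 5 regions, two-sided 0.05. Assumed, because the documents give no values: responder rates 15/25/33/33% (mean 26.5%), and two independent standardized baseline covariates with equal log-odds per SD. The comparison is the region-stratified CMH correlation test against a 1-df logistic score test for dose adjusted for region and both covariates, 3,000 runs per setting (simulation error about 0.8 points per power estimate). Variance explained is at the pooled rate of 26.5%.

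| Log-odds per SD | Variance explained | CMH power | Adjusted power | Difference | Less 0.9 |
|---|---|---|---|---|---|
| 0 | 0% | 72.4% | 73.3% | 0.9 | 0 |
| 0.3 | 3.3% | 71.9% | 74.3% | 2.4 | 1.5 |
| 0.5 | 8.5% | 73.6% | 77.6% | 4.0 | 3.1 |
| 0.7 | 14.8% | 73.3% | 79.8% | 6.5 | 5.6 |

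With no true trend, CMH rejected in 4.5 to 5.2% of runs and the adjusted test in 4.8 to 5.6%.

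**3. Removing the part not due to baseline.** The 0.9 points in the first row cannot come from baseline information. They reflect slight CMH conservatism and simulation noise, so the last column subtracts them. A separate run of 6,000 with size-matched critical values cut raw gains of 2.4, 4.0 and 6.5 points to 1.8, 2.8 and 5.4. Both routes give about 1 to 2 points at about 3% and about 5 to 6 at about 15%.

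**4. Sensitivity to rates and test.** A Wald test and other assumed rates (4,000 runs per setting) gave:

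- 15/22.5/30/30%: 60.3 to 61.4% at 1.5% of variance, 59.7 to 61.3% at 4.4%, 59.5 to 66.7% at 13.4%.
- 20/30/40/40%: 76.3 to 76.9% at 1.7%, 78.5 to 80.0% at 5.2%, 78.0 to 83.9% at 15.3%.

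The gains are therefore 1.1, 1.6 and 7.2 points, and 0.6, 1.5 and 5.9 points. With no association the two tests had the same power (60.5 and 60.4%; 78.6 and 78.6%). Gains of 12 to 14 points need baseline to explain 22 to 25% of variance, which nothing in the documents supports.

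**5. How predictive might baseline be?** Two illustrative models used the documents' SD of 1.73 with assumed baseline distributions and an assumed CSBM model. They gave variance explained of 0.05 to 1.0% and 0.25 to 2.1%, worth about one point or less.

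**The case against.** The strongest objection is that this exchanges one valid prespecified test for another. The CMH holds its level, it follows SAP 6.2, and the protocol already named it. Both responder components are relative to baseline (a CSBM increase of at least 1, a pain decrease of at least 30%), and eligibility narrows both covariates (mean pain at least 3.0; at most 6 CSBMs over the 14-day qualifying window). Baseline may therefore predict response only weakly. All of this stands, and it limits the size of the point.

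It does not remove the point. A 30% criterion cancels baseline only if pain change is roughly proportional to baseline. Take the active mean change of -1.975, SD 1.73 and an assumed mean baseline of 5.6. At baselines 3.5 and 8, the chance of a 30% drop is 70% and 40% if change does not depend on baseline, 54% and 60% at a slope of -0.35, and 47% and 67% at -0.5. Only near a slope of -0.3 does baseline become uninformative. The CSBM criterion is an absolute increase and has no proportional scaling.

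Four stronger readings are tempting but unsupported:

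- **That the plan certainly loses power.** The documents give no baseline-response association, so the loss may be nil.
- **That the baseline-adjusted SD shows the responder test was meant to be adjusted, or that the sample size is compromised.** That SD belongs to 12-week pain change, and the sample size does not rest on the responder.
- **That the other key models adjust for both baselines.** Each uses only its own.
- **That a missed responder trend blocks later tests.** SAP 6.1 makes p-values nominal, and SAP section 8(b) compares each DR dose with placebo whatever the trend result.

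**Conclusion.** This is a cheap improvement, not an error. The region-only CMH is a valid trend test for the 6/12 Week APC+1 Responder, but it leaves unused two baseline measures that the SAP already derives. The power forgone is essentially none if baseline does not predict response, about 1 to 2 points if it explains about 3% of outcome variance, and about 5 to 6 points at about 15%. The lower end is plausible because the endpoint is already referenced to baseline. These figures rest on assumed responder rates and an assumed strength of association. In the simulations, adjustment cost essentially nothing when baseline was uninformative.

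**What to change.** Before unblinding, amend SAP 7.9.1.1 for the 6/12 Week APC+1 Responder only:

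- Prespecify a 1-df score test for dose (scores 0, 1, 2, 3, the same spacing as the -3, -1, 1, 3 contrast) in a logistic model with region, baseline pain and baseline CSBM rate, fitted separately for DR1 with placebo and DR2 with placebo.
- Report standardized risk differences.
- Keep the region-stratified CMH alongside, and state in advance which of the two carries the key result.
- Record the change in SAP section 8.

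The cost is SAP wording and a few lines of code, with no new data. There are two small downsides. The odds ratio becomes conditional on baseline, which is why the risk difference is reported. The model should also not pass automatically to sparser endpoints such as the 9/12 Week and sustained responders through the cross-reference in SAP 7.9.2.2; those need a separation check or a stated fallback to CMH.

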### 7.9.1.2 Sensitivity Analyses of the Key Efficacy Parameters

If warranted, for selected efficacy endpoints, the potential impact of missing data on the estimates of treatment effect will be assessed using alternative statistical methods. The following sensitivity analysis approach based on multiple imputations (MI) will be utilized.

In order to characterize the extent of missing data associated with the key efficacy parameter, the number and percentage of patients with < 4 completed evening diaries will be presented by treatment group for the Intent-to-treat (ITT) Population for each week of the Treatment Period (Please refer to Section 7.8 for additional details).

Weekly data for a patient with less than 4 complete evening diaries will be classified as missing for that week. A pattern-mixture model using a placebo-based multiple imputation method (6) will be used as sensitivity analyses to explore the effects of missing data on the key efficacy endpoints and select other endpoints for the ITT Population.

The placebo-based MI imputes missing data after dropout (monotonic) based on the placebo group data using multiple imputation methodology for all subjects (including active treatment subjects).

The steps to implement Control-based MI are as follows:

1. **Create a Monotonic Dataset:** One-thousand (1000) datasets will be generated where missing outcome data at intermittent week (s) (non-monotonic) will be first imputed for each treatment using non-missing data from all subjects within the treatment group by a Monte Carlo Markov Chain (MCMC) imputation model with treatment, baseline score, geographic region and weekly score. The MCMC statement (mcmc chain=multiple impute=monotone) in the SAS PROC MI procedure will be used. As a result, each of the 1000 datasets will only have missing ending data, or a monotone missing data pattern.
2. For each of the 1000 datasets with monotonic missing data, the monotonic missing weekly data will be imputed one week at a time by a sequence of MIs, as follows.

Imputation will utilize data from all Placebo subjects and Active treatment with the week of interest (week currently being imputed) missing.

- a. For week 1, create two datasets: one containing all placebo patients and active patients with the week 1 value - missing, referred to as Mono\_imp1; one containing all other patients, referred to as Mono\_rest1.

- b. For Mono\_imp1, impute the missing values at week 1 utilizing Proc MI:

```
PROC MI data=mono_imp1 out=reg_imp1 nimpute=1 seed=XXXX;  
  By imputation; /*note 1000 imputation performed in step 1*/  
  Var base siteid change1 ;  
Run;
```

- c. Set Mono\_rest1 and reg\_imp1 Call this dataset IMP1.

- d. Repeat Steps 2a-2c for weeks 2 – 12, respectively

Note: for Week i,  $i > 1$ ,

```
PROC MI data=mono_impi out=reg_impi nimpute=1 seed=XXXX;  
  By imputation; /*note 1000 imputation performed in step 1*/  
  Var base siteid change1 change2 . . . change(i-1) change(i);  
Run;
```

3. Analyze each of the 1000 imputed complete datasets.
  - a. For continuous endpoints, perform same statistical analyses (MMRM or ANCOVA) as described for observed case.
  - b. For responder endpoint:
    - a. Using the CSBM and Abdominal Pain data imputed above, recalculate the responder
    - b. For each imputed dataset, perform Cochran-Mantel-Haenszel (CMH) analyses as described above.
4. Estimation and Inference of the MI datasets will be performed using Rubin's combination rules (7) as implemented through the MIANALYZE procedure in SAS.

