## **6. STATISTICAL METHODS**

### **6.1 GENERAL METHODS**

All summaries will be presented by treatment unless specified otherwise. Descriptive statistics including the number of patients, mean, standard deviation (SD), median, minimum, and maximum will be calculated for continuous variables. Frequencies and percentages for each category will be calculated for categorical variables. Percentages will be based on the total number of non-missing values. The number missing will be presented, but without a percentage. All hypothesis tests will be two-sided with a 5% significance level, and 95% confidence intervals will be used, unless stated otherwise. There is no adjustment for multiplicity; p-values will be reported as nominal.

All statistical analyses will be performed using SAS Version 9.3 (or later) for Windows.

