#### **6.5 MULTICENTER STUDIES**

This study is being conducted in approximately 80 centers. Due to the potential of small numbers of patients per center, data will be pooled by center into the following 5 geographic regions (as listed in [Table 7](#)): Northeast, Southeast, Midwest, Southwest, and West.

All analyses using trial center will use this 5-category geographic region variable.

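### The placebo-based imputation in SAP 7.9.1.2 enters site ID as a number instead of region, imputes pain and CSBM separately, and names no poolable quantity for the CMH trend test

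*SAP*

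**What the plan says.** SAP 6.5 pools about 80 centers into five regions and states: "All analyses using trial center will use this 5-category geographic region variable". Section 9.3 repeats the rule.

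SAP 7.9.1.2 describes the multiple imputation in four steps.

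- Step 1 fills intermittent gaps by MCMC, using an "imputation model with treatment, baseline score, geographic region and weekly score".
- Step 2 imputes the remaining weeks one at a time from a data set of all placebo patients plus the active patients who lack that week. The Week 1 code lists "Var base siteid change1". The code for later weeks keeps the same baseline and site ID and adds the earlier changes of the same series. Neither block has a CLASS or MONOTONE statement.
- Step 3 covers the responder endpoint: "Using the CSBM and Abdominal Pain data imputed above, recalculate the responder", then "For each imputed dataset, perform Cochran-Mantel-Haenszel (CMH) analyses as described above".
- Step 4 pools by Rubin's rules "as implemented through the MIANALYZE procedure in SAS".

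Section 7.9.1.1 makes the responder trend test a CMH correlation statistic controlling for region. Section 7.9.1 defines a Weekly APC +1 Responder as a patient who meets the pain and the CSBM criterion in the same week.

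**The concern.** There are three separate gaps between the stated method and what a programmer would run.

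1. A variable in the VAR list without CLASS is treated as numeric. Site numbers are labels, so a straight line through them has no meaning, and region is in effect left out of the step 2 model.
2. The composite depends on pain and CSBM improving together. If each series is imputed without sight of the other, part of that association is lost in the imputed weeks, and fewer imputed weeks meet both criteria.
3. Rubin's rules combine an estimate and its standard error. A CMH correlation chi-square supplies neither, so the programmer has to choose a method after the data are in.

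Protocol 5.7.7 promises both multiple imputation and LOCF as sensitivity analyses of the key endpoints. The SAP specifies LOCF only for EQ-5D-3L (Section 7.12.2), so this imputation is the only missing-data sensitivity analysis that it sets out for the key endpoints. SAP Section 8, item c, also sends the added Sustained Responder endpoints through Section 7.9.1.2. Those depend on Weeks 9 to 12, which dropouts lack.

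**Working it through.** **The plan's own figures.** The imputation section states no numerical result. The figures at hand are the powers in SAP Section 4.

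- Trend: the contrast is -3(-1.196) - 1(-1.586) + 1(-1.975) + 3(-1.975) = -2.726. Its standard error is 1.73 × √(20/65) = 0.960, and the ratio is 2.841. Power is Φ(2.841 - 1.960) = 0.811, against 81% stated.
- Pairwise: 0.78 / (1.73 × √(2/65)) = 2.570. Power is Φ(2.570 - 1.960) = 0.729, against 73% stated.

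Both reproduce, and neither uses the imputation.

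**1. Site ID in place of region.** Assume 80 sites numbered without regard to region. A linear term in an unrelated label explains on average 1/79 = 1.3% of the between-region variance. A simulation gave a mean of 1.3% and a 95th percentile of about 5%.

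For the size, assume a regional SD of 0.3 pain points and 20% dropout, so 13 of 65 patients per arm. With independent errors of one regional SD in each imputed value, the arm mean moves by about 0.3 × √13 / 65 = 0.017 points. If all 13 dropouts came from one region, the shift would be 0.3 × 13 / 65 = 0.06. The planning difference is 0.78.

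**2. Separate imputation.** The documents give neither the pain-CSBM correlation nor a dropout rate, so the following are assumptions: a bivariate normal model over 12 weeks, week-to-week ICC 0.7, weekly responder rates of 45% (pain) and 40% (CSBM), correlation 0.3 to 0.6, and dropout after Week 1 to 6.

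Each series is drawn given its own k observed weeks. The variance of the patient's level that remains undetermined is ICC(1 - ICC) / (k·ICC + 1 - ICC):

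- k = 1: 0.21 / 1.0 = 0.21, which is 30% of 0.7
- k = 6: 0.21 / 4.5 = 0.047, which is 7% of 0.7

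The patient's own history therefore carries much of the association into the imputed weeks. What is lost is the dependence in the undetermined part and in the weekly residuals.

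Compared with joint imputation, the 6/12 APC +1 rate among dropouts falls by 0.7 points (correlation 0.3, dropout after Week 6) to 5.2 points (correlation 0.6, dropout after Week 1). Another simulation gave about 0.9 to 5 points. At correlation 0 there is no loss. At 20% dropout the fall per arm is 0.2 × 0.7 = 0.14 to 0.2 × 5.2 = 1.04 points.

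A milder model treats the patient's level as known, so that only weekly residual dependence is lost. At correlation 0.6 it gives:

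| Weeks imputed | Joint | Separate | Loss (points) |
|---|---|---|---|
| last 4 | 0.2598 | 0.2503 | 1.0 |
| last 8 | 0.2627 | 0.2399 | 2.3 |
| last 10 | 0.2608 | 0.2352 | 2.6 |

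**3. Pooling.** Setting Section 7.9.1.1 beside steps 3 and 4, the quantity from each data set is a one-degree-of-freedom chi-square, and the pooling tool needs an estimate with a standard error. No sentence links them. The gap can be closed. With ordinary imputation, 200 imputations and an assumed 5 to 30% of information missing, Rubin's rules rejected a true null 4.9 to 5.0% of the time on the signed root of the statistic, and 5.1 to 5.3% on its Wilson-Hilferty transform. These runs did not use placebo-based imputation.

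**The case against.** The strongest reply is that this is template code for a conditional analysis. The seed is a placeholder and the week lists are elided, so nobody can run it verbatim. Sections 6.5 and 9.3 already govern how center is used, and Section 9.3 even calls the pooled variable a five-category center variable, so the site ID in the code may be a recoded region. That softens the point without removing it: without CLASS, five region codes would still enter as a linear score.

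The text never promises joint imputation of pain and CSBM. Separate imputation is inferred from the single baseline and single change series, so it is a modelling weakness and not a contradiction. This is right. It is also right that the loss occurs in placebo as well as active arms, so no bias in the treatment contrast has been shown.

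On pooling, for the pairwise comparisons a log common odds ratio with its standard error can be pooled directly. The gap concerns the trend statistic.

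Four stronger readings are tempting, and the documents do not support them.

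- A reader might infer that the code fails to deliver placebo-based imputation. It does deliver it: the step 2 data sets match the prose.
- A reader might infer that imputed pain and CSBM values bear no relation to each other. Each draw conditions on that endpoint's own history, and the two histories are correlated within a patient.
- A reader might infer that CMH results can never go through Rubin's rules. They can, after a standard transformation or as an estimate with a standard error.
- A reader might infer an inflated type I error from averaging chi-squares across imputations. The SAP does not specify averaging. When averaging was simulated under placebo-based imputation, a true null was rejected only about 2.5 to 4.4% of the time, because imputing active dropouts from placebo data pulls the arms together.

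**Conclusion.** The point holds as a minor correction to one sensitivity analysis.

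- The site ID term is wrong as written, because it contradicts step 1 and Sections 6.5 and 9.3. Its effect is small, about 0.02 points per arm under the assumed regional SD and dropout.
- Separate imputation lowers the imputed 6/12 APC +1 rate among dropouts by about 1 to 5 points. This rests on an assumed correlation of 0.3 to 0.6, ICC 0.7 and dropout after Week 1 to 6. There is no loss at correlation 0.
- Step 4 cannot be run as written for the CMH correlation statistic, because a step is missing.

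The SAP runs this analysis only if warranted and for selected endpoints. The main responder analysis already counts weeks after discontinuation as non-response (Section 6.3).

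**What to change.** Three edits to SAP 7.9.1.2:

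1. In step 2, replace site ID with region, declare it in a CLASS statement, and add a MONOTONE REG statement.
2. Impute the weekly changes in pain and CSBM in one model, with both baselines and both histories in the variable list. The SAP already sets a week to missing when it has fewer than four complete evening diaries. That rule applies to both endpoints, so ordering the variables by week keeps the pattern monotone.
3. In steps 3 and 4, name the quantity to pool for the responder trend test: per imputation, save either the dose-trend log odds ratio with its standard error or the Wilson-Hilferty-transformed CMH statistic, and pass that to MIANALYZE.

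The cost is SAP wording and code, with slightly larger imputation models. No new data are needed.
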